11.3 Measurement of Response

11.3.1 Baseline Documentation of Target lesions

All treated tumors (GTV1-5) should be identified as the target lesions and recorded and measured at baseline and with each follow-up imaging evaluation. The longest diameter (LD) for the target lesion will be calculated from the treatment planning CT scan using pulmonary windowing and reported as the baseline LD. For follow-up assessment, diagnostic CT scans pulmonary windows are preferred as the method of evaluation for response. Cases in which it is indeterminate whether consolidation represents residual tumor or treatment effect, it should be assumed that abnormalities are residual tumor

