11.3.2 Evaluation of Target and Involved Lobe Lesions

Complete Response(CR)	Disappearance of the target lesion; ideally, this determination will be made based on CT image evaluation.
Partial Response(PR)	At least a 30% decrease in the LD of the target lesion, taking as reference the baseline LD; ideally, this determination will be made based on CT image evaluation.
Stable Disease (SD)	Neither sufficient shrinkage to qualify for CR/PR above nor sufficient increase to qualify for LE below, taking as reference the smallest LD since the treatment started
Local Enlargement(LE)	At least a 20% increase in the LD of target lesion, taking as reference the smallest LD recorded since the treatment started; Ideally, this determination will be made based on CT image evaluation.
Primary Tumor Failure (PTF)	Refers to the primary treated tumor after protocol therapy and corresponds to meeting both of the following two criteria: 1) Increase in tumor dimension of 20% as defined above for local enlargement (LE); 2) The measurable tumor with criteria meeting LE should be avid on Positron Emission Tomography (PET) imaging with uptake of a similar intensity as the pretreatment staging PET, OR the measurable tumor should be biopsied confirming viable carcinoma. For outcome analysis, Marginal Failures (MF; see below) will also be counted as PTF; however, they should be distinguished specifically as MF, not PTF, on all report forms. The EORTC criteria for post-treatment PET evaluation will be used as a basis for evaluation in cases more difficult to assign as to whether the uptake is pathological for cancer recurrence vs. inflammation. ⁴⁶
Marginal Failure (MF)	Refers to the appearance after protocol therapy of a measurable tumor appearing since treatment within 1.0 cm of the treated PTV (see Section 6.4) and meeting the following two criteria: 1) Enlarging tumor dimensions corresponding to a 20% increase in the longest diameter compared to initial appearance on imaging evaluation. Ideally, this determination will be made based on CT image evaluation; 2) The measurable tumor within 1.0 cm of the treated PTV should be avid on Positron Emission Tomography (PET) imaging with uptake of a similar intensity as the pre-treatment staging PET, OR the measurable tumor should be biopsied confirming viable carcinoma.
Primary Tumor Control	The absence of Primary Tumor Failure.

(PTC)	

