Involved Lobe Failure	Refers to the appearance of lung cancer after protocol therapy within the anatomical boundaries of the lobe in which the primary tumor arose (involved lobe). The measurable tumor apart from the primary tumor but within the involved lobe should meet criteria for LE, should be avid on Positron Emission Tomography (PET) imaging with uptake highly suspicious for cancer (e.g., SUV>3-5), OR the measurable tumor should be biopsied confirming viable carcinoma. Failure outside of the involved lobe (uninvolved lobes) will be considered metastatic disseminated (distant) failures. Local Failure Refers to either primary tumor failure or involved lobe failure or both.
Local Control (LC)	The absence of Local Failure

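### Local control as defined in 11.3.2 fails on a confirmed new same-lobe metastasis and lets untested growth default to control; the treated-lesion rate is defined but not named as the endpoint

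*Combined protocol and SAP*

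**What the plan says.** **Objective.** Local control is the first secondary objective (2.1.2), and the hypothesis in 2.1 names it in comparison with resection. Section 12.3 sends both local and regional recurrence to 11.3.2, lesion by lesion. Section 13.2 lists local and regional control. Section 12.4 asks for crude locoregional recurrence rates.

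**Composite.** Under 11.3.2, "Local Failure Refers to either primary tumor failure or involved lobe failure or both", and Local Control is its absence. On Involved Lobe Failure: "The measurable tumor apart from the primary tumor but within the involved lobe should meet criteria for LE", with suspicious PET uptake or a positive biopsy as confirmation. Disease in other lobes is classed as distant. No category is called regional.

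**Treated-lesion measure.** Primary Tumor Control is "The absence of Primary Tumor Failure". A new tumor within 1.0 cm of the PTV is a Marginal Failure, and "For outcome analysis, Marginal Failures (MF; see below) will also be counted as PTF".

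**Confirmation.** Primary Tumor Failure needs two things: growth of at least 20%, and either a positive biopsy or a lesion that "should be avid on Positron Emission Tomography (PET) imaging with uptake of a similar intensity as the pretreatment staging PET". Marginal Failure has the same two-part structure. Section 11.2.2 leaves PET and biopsy at suspected progression to the physician, with biopsy recommended. A footnote to 11.1 allows the baseline PET to be omitted if insurance does not cover it.

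**Related rules.** For consolidation that cannot be told from treatment effect, 11.3.1 says "it should be assumed that abnormalities are residual tumor". Section 11.3.2 adds: "The EORTC criteria for post-treatment PET evaluation will be used as a basis for evaluation in cases more difficult to assign".

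**The concern.** A reader of the final report will probably take local control to mean that the irradiated lesions stayed controlled. The defined rate departs from that in two ways.

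First, it charges new disease elsewhere in the lobe to the local result. Section 12.3 speaks of regional recurrence, but the section it points to has no regional class. Same-lobe disease sits inside local failure and everything beyond the lobe is distant.

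Second, it depends on which enlarging lesions were tested. Control is the absence of a confirmed failure, and there is no class for growth that was not investigated.

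The introduction says the study is meant to document local control for sarcoma lung metastases. At stake is whether the pilot's single rate can be read that way. Because the two effects run in opposite directions, a plausible-looking figure gives no reassurance.

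**Working it through.** **1. Apply the definitions.** Primary Tumor Failure (PTF) = growth of at least 20% AND (PET or biopsy confirms). Local failure = PTF OR Involved Lobe Failure.

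| Growth ≥20% | PET or biopsy confirms | Confirmed new same-lobe tumor | PTF | Local Control |
|---|---|---|---|---|
| no | – | no | no | yes |
| no | – | yes | no | **no** |
| yes | no, or never done | no | no | **yes** |
| yes | no, or never done | yes | no | no |
| yes | yes | no | yes | no |
| yes | yes | yes | yes | no |

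The second row is a controlled lesion reported as local failure. The third row includes an enlarging, untested lesion reported as control.

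**2. Inputs for size.** The plan states no local control target, so there is no figure of its own to reproduce. From the documents:
- About 40 tumors (Schema).
- Two-year local control of 77.9% (pooled literature review), 88% (retrospective sarcoma series) and 96% (phase I/II lung metastasis trial), all from 1.0 Introduction. They serve only as trial values for true treated-lesion control. The documents do not say how those sources defined it.

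Assumed, with no source in the documents:
- q = share of treated lesions with a confirmed same-lobe event
- u = share of true failures never tested
- s = share of truly controlled lesions showing unresolved 20% growth

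**3. Formula.** With f = 1 − true control and independence, reported Local Control = [1 − f(1 − u)] × (1 − q).

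At 88% true control (f = 0.12; 35.2 of 40):
- Lobe rule alone, q = 0.20, u = 0: 0.88 × 0.80 = 0.704 (28.2 of 40). Without independence the bounds are 1 − 0.12 − 0.20 = 0.68 (no overlap) and 1 − 0.20 = 0.80 (full overlap).
- Lobe rule alone, q = 0.05: 0.88 × 0.95 = 0.836.
- Untested growth alone, u = 0.50, q = 0: 1 − 0.12 × 0.50 = 0.94 (37.6 of 40).
- Both, q = 0.05, u = 0.50: 0.94 × 0.95 = 0.893 (35.7 of 40).
- Both, q = 0.20, u = 0.50: 0.94 × 0.80 = 0.752.

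**4. Other trial values.**

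| True control | q = 0.20 alone | u = 0.50 alone | q = 0.05 and u = 0.50 | Net, last case |
|---|---|---|---|---|
| 77.9% | 62.3% | 89.0% | 84.5% | +6.6 points |
| 88% | 70.4% | 94.0% | 89.3% | +1.3 points |
| 96% | 76.8% | 98.0% | 93.1% | −2.9 points |

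With q and u held fixed, the net sign changes with the true rate.

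**5. Behavior of a rate that counts unresolved growth as failure.** If every true failure shows 20% growth, the rate is 0.88 × (1 − s): 88.0%, 83.6% and 79.2% at s = 0, 0.05 and 0.10. At u = 0.50 and no same-lobe counting, the confirmed-only rate is 94%, so the pair brackets the true 88%.

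**The case against.** **The composite is explicit and prespecified.** This stands. A reader might infer that the definition is simply an error. The documents do not support that: no passage says local control must mean the treated lesion only, and a lobe-based concept is arguable when the comparison is with resection. The defect is narrower. Two defined rates exist, the endpoint sections do not say that the treated-lesion one is wanted, and the regional recurrence in 12.3 has no definition to point to.

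**The treated-lesion rate is not lost.** Also true. Primary Tumor Control is defined, Marginal Failure must be distinguished on report forms, and 11.3.1 requires each treated tumor to be measured at each follow-up imaging. The rate can be recovered, but no endpoint section asks for it.

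**No sentence says untested growth is control.** Correct; a reader might take it as a stated rule, and it is not. It follows because failure needs both criteria and control is the absence of failure. The residual-tumor presumption in 11.3.1 can affect the measured diameter but does not supply the PET or biopsy criterion. The EORTC sentence concerns how to read PET uptake, so it cannot classify a lesion with no follow-up PET. The documents do not show whether it settles a lesion with no baseline PET.

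**Confirmation protects specificity.** It does. Section 6.8.3 warns that collapsed lung can be reported as progression while the tumor is stable or shrinking. That is a reason to keep the confirmed rate and add a second one beside it.

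**Double counting.** A reader might infer that one new same-lobe tumor fails every treated lesion in that lobe. Section 12.3 can equally mean that each recurrent lesion is classified once. The documents do not decide, so no loss is claimed on that account.

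**Conclusion.** The point holds as a should-fix matter of endpoint definition. Both classifications follow directly from 11.3.2, and confidence in them is high. Their size is not known. The shifts shown (88% reading 70%, 94% or 89.3%) rest on assumed same-lobe and untested shares, on independence, and on two-year figures of unstated definition. Those figures are treated as crude proportions of about 40 tumors, with no allowance for death or incomplete follow-up.

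A reader might infer that the reported rate will be too low because of the lobe rule, or too high because of untested growth. Neither can be derived from the documents. Nor do they support a claim that the trial's main conclusion is at risk: local control is secondary, no decision rule rests on it, and the toxicity objective is untouched.

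**What to change.** 1. In 2.1.2, 12.3 and 13.2, name Primary Tumor Control, with Marginal Failure counted as failure, per treated lesion, as the local control rate.
2. Report Involved Lobe Failure separately as regional failure, once per event. Report the combined locoregional rate of 12.4 per patient, so that its unit is defined.
3. Report local control two ways:
   - Rate 1: failures confirmed under 11.3.2.
   - Rate 2: also counting as failure any treated lesion or marginal tumor that meets the 20% growth criterion and either (i) had no PET or biopsy, or (ii) had an avid follow-up PET, no baseline PET for comparison, and no biopsy result.
4. Give the number of lesions in groups (i) and (ii). A lesion with both PETs whose uptake does not meet the similarity criterion is classed by 11.3.2 as it stands. If the EORTC criteria are meant to settle group (ii), say so.
5. As an editorial correction only, replace the lung-cancer and carcinoma terms in 11.3.2 with sarcoma terms, and refer to the lobe containing the treated lesion.

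The cost is wording in four sections and one extra tabulated rate, from CT scans and measurements already required. PET and biopsy stay discretionary. The downside is that rate 2 may count some treatment effect as failure, the caution raised in 6.8.3, which is why both rates are shown.

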SBRT is increasingly being used to treat pulmonary metastases (11-17). This is particularly appealing as the toxicity is low, control rates are high and in many cases invasive procedures can be avoided. Large hypofractionated doses are used to treat metastatic lesions. SBRT can be safely administered because the volume of each lesion is small with tight margins. Moreover, many beams are utilized, so that a small fraction of the total dose is administered through each beam, thereby effectively minimizing toxicity through the trajectory of the beam. However, all beams coalesce at the target and result in a larger, summed, dose (11, 20-21). Many studies have evaluated outcomes and toxicity in patients who have undergone SBRT for pulmonary oligometastasis from various tumor primaries (12). Lesions are usually central or peripherally located and a small proportion is comprised of sarcoma primaries. Nonetheless, crude local control rates when utilizing this method of treatment are between 67-100% and 2-year survival ranging between 32-87% (11, 13-19). Toxicity was acceptable with very few developing grade 3 or 4 complications.

Although local control of pulmonary metastases with SBRT is high, there is no prospective data evaluating control with SBRT for pulmonary metastases from soft tissue sarcomas. This is a prospective study to document the local control rates with SBRT specifically for pulmonary metastases from soft tissue sarcoma. This study will prospectively document acute and late toxicity, quality of life (QoL), tumor control, and survival.

Siva, et al reported a literature review to critically review the effects of SBRT for treatment of pulmonary metastases. Data from 334 patients combined from 13 publications reported a 2 year weighted local control of 77.9% (12). Rusthoven et al conducted a multi-institutional Phase I/II trial of SBRT for patients with 1-3 lung metastases up to 7cm. Two year local control was 96% (19).

The University of Rochester retrospectively reviewed control rates of 74 sarcoma pulmonary metastases in 52 patients from 1990-2006 (22). Sixteen patients had surgical procedures for management. Fifteen patients were treated to 74 lesions with SBRT. The preferred dose was 50 Gy in 5 fractions. Two-year local control was 88% for all patients treated with radiation although with exclusion of one patient's lesion treated with 30 Gy in 10 fractions, local control was 97%. There was no \geq grade 3 pulmonary toxicity.

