11.0 PATIENT ASSESSMENTS

11.1 Study Parameters

Assessments	Pre-Study Entry	During Therapy (each fraction)	At 4-6 Weeks (+/- 1 month) after SBRT	Every -6 months (+/- 1 month) after RT for 12years
History/physical,	X		X	X
Zubrod PS	X	X	X	X
Toxicity Evaluation		X	X	X
QoL (FACT-L)	X			X
CT of the Chest	X*			X
PET/CT	X**			If Needed***
PFTs	X (not required)			X** (not required)

PFTs are not required for this protocol. PFTs may be done pre-treatment and 3 months after therapy and as clinically indicated.

*CT scan- within 6-8 weeks of study entry

** PET/CT -may be omitted if not covered by insurance although is recommended to assist in treatment planning and to assess the appropriateness of study therapy.

***PET/CT-to be done at discretion of physician

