12. DATA COLLECTION

12.1. Study Design:

This is a non-randomized Phase II pilot protocol to determine the feasibility, toxicity, and disease control (overall and progression-free survival) using SBRT in patients with pulmonary oligometastatic disease from soft tissue sarcoma primaries.

12.2. Primary Endpoint:

The primary aim of this study is to assess toxicity and quality of life from SBRT. All patients will be followed for the primary endpoint for a minimum of 3 years. Based on historical data, we expect there will be minimal toxicity, both acute and long term. Adverse event rates will be compared at specific time points (3, 6 and 12 months after completion of SBRT). Quality of life will be measured with the FACT-L questionnaire (Appendix IV).

12.3. Secondary Endpoint:

The secondary objective of this study is to assess local and regional control, progression-free survival and overall survival. Local and regional recurrence will be defined for each lesion per criteria in section 11.3.2. Disease-free survival is defined as the time from randomization until documented disease-recurrence or death, whichever occurs first. Patients who are disease-free and alive at the time of analysis will be censored at the time of their last follow-up. Patients will be followed for disease-free survival for a minimum of 3 years.

12.4. Endpoint Analysis:

Crude rates of locoregional recurrences will be documented as well as the time to development of recurrence or relapse. Time of last follow-up or death will also be noted. This will allow us to calculate progression free and overall survival rates.

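### Local control is not tied to post-SBRT imaging, so lesions that were never scanned, or not scanned again after an early CT, can count as controlled and the rate can be overstated

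*Combined protocol and SAP*

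**What the plan says.** Section 11.3.2 defines control negatively. Primary Tumor Control is "The absence of Primary Tumor Failure" and Local Control is "The absence of Local Failure", where local failure means primary tumor failure, involved lobe failure or both. Failure needs positive evidence. Primary tumor failure "corresponds to meeting both of the following two criteria": a measured 20% enlargement, and PET avidity or a positive biopsy. Involved lobe failure also rests on imaging or biopsy.

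Section 12.3 applies the criteria lesion by lesion. Section 12.4 gives the analysis: "Crude rates of locoregional recurrences will be documented as well as the time to development of recurrence or relapse". It adds: "Time of last follow-up or death will also be noted", and says that this serves progression-free and overall survival. The only censoring rule, in Section 12.3, belongs to disease-free survival: "Patients who are disease-free and alive at the time of analysis will be censored at the time of their last follow-up". Section 13 adds no method for local control.

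On imaging, the Section 11.1 table marks post-treatment chest CT only in the column headed "Every -6 months (+/- 1 month) after RT", not at the 4-to-6-week visit. Section 11.2.2 asks for a chest CT before each visit, and Section 11.2.1 puts the first visit at 4 to 6 weeks.

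**The concern.** A failure can be recorded only if someone looked. A patient who dies, is lost or becomes too ill before the first follow-up CT has no image on which growth could be measured, yet each treated lesion meets the definition of controlled. The same applies later: a lesion scanned once at 4 to 6 weeks in a patient who dies at 5 months also counts as controlled, on a scan that says little about durable control.

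Relative to the scanned lesions, this can only raise the rate, and the effect grows as survival worsens. The hypothesis in Section 2.1 is local control similar to resection, and the Introduction sets the study beside published control rates, so the figure will be read comparatively. Adding a time point to the crude rate would not solve this, because lesions with no evaluation would stay in the controlled count.

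**Working it through.** **Plan's own figures.** No target, precision or power is stated for local control. The sample size is accrual arithmetic: (5 + 5) patients per year × 2 years = 20, which matches. With 40 expected tumors, that is 40/20 = 2 lesions per patient.

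**Inputs from the Introduction.** For survival, "2-year survival ranging between 32-87" percent across published series. For control: 67% (lowest crude rate cited), 77.9% (pooled 2-year figure from the literature review) and 88% (2-year figure from the sarcoma series).

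**Assumptions.** Constant death hazard from the end of SBRT; 2 lesions per patient; failure risk unrelated to death; every surviving patient is scanned on time.

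**Step 1: deaths before any CT.** With 2-year survival S, the share dying by time t is u = 1 − S^(t/2 years).
- First CT at 6 months: 1 − 0.87^0.25 = 3.4%; 1 − 0.32^0.25 = 24.8%.
- First CT at 6 weeks: 1 − 0.87^(6/104) = 0.8%; 1 − 0.32^(6/104) = 6.4%.

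**Step 2: effect on the rate.** If control among scanned lesions is L, the literal definition over all treated lesions gives L(1 − u) + u, an inflation of u(1 − L). For example, 0.779 × 0.752 + 0.248 = 83.4%.

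| First CT | Never scanned | Of 20 patients | Of 40 lesions | 67% reads as | 77.9% reads as | 88% reads as |
|---|---|---|---|---|---|---|
| 6 months | 3.4% to 24.8% | 0.7 to 5.0 | 1.4 to 9.9 | 68.1% to 75.2% | 78.7% to 83.4% | 88.4% to 91.0% |
| 6 weeks | 0.8% to 6.4% | 0.2 to 1.3 | 0.3 to 2.5 | 67.3% to 69.1% | 78.1% to 79.3% | 88.1% to 88.8% |

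The documents give no dropout rate. If 10% loss is assumed on top of death before a 6-month CT, u = 1 − (1 − 0.034)(0.90) = 13.1% up to 1 − (1 − 0.248)(0.90) = 32.3%, and 77.9% reads as 80.8% to 85.0%.

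**Step 3: crediting control after the last look.** An early CT does not remove the effect of later deaths. Let failure and death have constant hazards f = −ln(L)/2 and d = −ln(S)/2 per year, with failures in living patients seen at once. The share of all lesions with recorded failure by 2 years is f/(f + d) × (1 − L·S). For L = 0.779:
- S = 0.87: 20.7% failed, so 79.3% counted as controlled (+1.4 points).
- S = 0.32: 13.5% failed, so 86.5% counted as controlled (+8.6 points).

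This compares with the 77.9% that would be seen if nobody died, and does not depend on the date of the first CT.

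**Step 4: one dataset, three answers.** Take 40 lesions, 10 never scanned, and 7 failures among the 30 scanned. The rate is 33/40 = 82.5% on the literal definition, 23/30 = 76.7% among scanned lesions, and 23/40 = 57.5% if unscanned lesions count as failed. The plan does not choose among them.

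**The case against.** The strongest reply is that the plan never says unscanned lesions are controlled. A reader might infer that from the definition, but Section 12.4 sets no denominator, and it also records time to recurrence, so a properly censored estimate remains possible. That stands: the documents support saying that control can be overstated, not that it will be.

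A reader might also infer that no follow-up CT is required. That is wrong. CTs are scheduled, and Section 11.3.1 has lesions measured at each one. What is missing is the link from that schedule to the definition. Nor can 6 months simply be taken as the first CT: Section 11.2.2 points to 4 to 6 weeks, which brings deaths before any scan down to between 0.8% and 6.4%.

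It is tempting to read Section 12.4 as ending local-control follow-up at last contact or death. The text ties that date to progression-free and overall survival; for local control the plan is silent.

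The upper end also leans on 32% survival from series of mixed primaries. This trial requires Zubrod 0–2 and 3 months without extra-pulmonary progression, so early deaths may be fewer. Finally, sampling error is large: the exact 95% interval for 33/40 is 67% to 93%. These points limit the size. They do not remove a bias whose direction, relative to scanned lesions, is known.

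**Conclusion.** The point holds as a gap in the definition and analysis of a secondary endpoint, and it should be corrected. For deaths before any CT, the inflation at 77.9% control is 0.8 to 5.5 points with a first CT at 6 months and 0.2 to 1.4 points with a first CT at 6 weeks. It is zero if every lesion is scanned. Crediting control after the last scan can add to this under either schedule. All figures rest on constant hazards, the cited survival range, and failure risk unrelated to death or loss.

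Two stronger readings are not supported. Local control is not designated the main efficacy endpoint: it is one of four secondary objectives in Section 2.1.2, and acute toxicity is primary. Nor can bias against the published rates be claimed, since the documents do not say how those series handled unscanned lesions.

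**What to change.** In Sections 11.3.2 and 12.4:

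- Estimate lesion-level time to local failure, with follow-up for local control ending at the last post-SBRT chest CT, not at last contact or death. This is the main change. Requiring at least one CT is not enough by itself, because a lesion scanned once at 4 to 6 weeks would still be credited as controlled. Allow for several lesions per patient.
- For any crude rate, use as denominator the lesions with at least one post-SBRT chest CT. Report how many lesions were not scanned and why (death, loss, too ill), with bounds counting them all as controlled and all as failed.
- If a cumulative incidence with death as a competing risk is preferred, label it as incidence of failure, not as the proportion of lesions controlled.
- Reconcile the Section 11.1 table with Section 11.2.2 on when the first follow-up CT is done.

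The cost is a few sentences and no new assessments, since the CTs are already scheduled and lesions are measured at each. The downside is a smaller denominator and a slightly less favorable local control figure.
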